11.1.3 ASSESSMENT OF EXPECTEDNESS

A reasonable possibility of a relationship conveys that there are facts, evidence and/or arguments to suggest a causal relationship, rather than a relationship that cannot be ruled out.

- Expected: An adverse reaction, the nature or severity of which is consistent with the applicable Reference Safety Information in the Summary of Product Characteristics for an approved medicinal product
- Unexpected: An adverse reaction, the nature or severity of which is not consistent with information in the relevant source document

11.1.4 FOLLOW-UP OF SAES

After the initial SAE report, the Investigator is required to proactively follow each participant and provide further information to the Sponsor on the participant's condition. All SAEs documented at a previous visit/contact and are designated as ongoing, will be reviewed at subsequent visits/contacts. All SAEs will be followed until resolution, until the condition stabilises, until the event is otherwise explained, or until the participant is lost to follow-up. Once resolved, the adverse event log will be updated. The Investigator will ensure that follow-up includes any supplemental investigations as may be indicated to elucidate the nature and/or causality of the SAE. This may include additional laboratory tests or investigations, histopathological examinations, or consultation with other health care professionals. New or updated

information will be recorded on the originally completed SAE form, with all changes signed and dated by the Investigator. The updated SAE form should be resent to the Sponsor.

11.1.5 Post-study saes

A post-study SAE is defined as any event that occurs outside the SAE detection period. Investigators are not obligated to actively seek SAEs in former study participants. However, if the Investigator learns of any SAE, including death, at any time after a participants has been discharged from the study, and he/she considers the event reasonably related to the investigational product, the Investigator will promptly notify the Sponsor.

11.1.6 SAEs

SAEs that lead to hospitalisation within 90 days of randomisation will be source data for the primary endpoint and will detail cause of hospitalisation to determine if this was related to COPD or not.

11.2 ADVERSE EVENT PROCESSING RESPONSIBILITIES

The Trial Statistician will report relevant adverse events to the Data Monitoring Committee.

12. ETHICS APPROVAL

This protocol and related documents will be submitted for review to Health Research Authority (HRA), and Research Ethics Committee (REC).

12.1 PROTOCOL AMENDMENTS AND VERSION CONTROL OF STUDY DOCUMENTS

The Trial Manager will be responsible for preparing and submitting protocol amendments to the Sponsor and ethics committee/HRA.

The Trial Manager will be responsible for updating the ISRCTN register subsequent to relevant protocol amendments.

13. STATISTICAL METHODS

13.1 **PRIMARY OUTCOME**

1. Time to first all-cause readmission within 90 days of discharge from hospital. The day of discharge will be the 1st day in the countdown to 90-day timepoint

13.2 **SECONDARY OUTCOMES**

- Time to and frequency of COPD-related readmissions at 30 and 90 days
- Days alive and out of hospital at day 90
- Time to and frequency of all COPD exacerbations at days 30 and 90
- Cumulative systemic oral corticosteroids use over 90 days, measured as proportion of period used and number of occasions used
- Cumulative systemic antibiotic use over 90 days, measured as proportion of period used and number of occasions used
- Health care contacts at baseline, days 90 and 180, and 1 year
- All cause readmission at 30 days

- All cause-, cardiovascular- and COPD- related mortality at day 90 and over 12 months
- Quality of life (COPD assessment Test (CAT) score and EQ-5D-5L) at baseline, days 90 and 180, and 1
 year
- Incremental cost-effectiveness ratio (ICER, a ratio of the additional cost divided by the additional effectiveness of SRP compared to UC) at days 90 and 180 and 1 year
- Qualitative description of usual care
- Qualitative examination of fidelity to and adaptation of the plan in the intervention arm
- Serious adverse events
- Antimicrobial resistance

13.3 SAMPLE SIZE JUSTIFICATION

A sample size of 1400 participants randomised has been chosen to achieve a target of 515 primary outcome events. Population estimates of the 90-day and 30-day all-cause readmission rates of 43% and 23%⁴²respectively have been reported previously. In the absence of a minimum clinically important effect size defined for the 90-day all-cause readmisstion primary outcome, we performed a national survey of respiratory COPD secondary care specialists via the British Thoracic Society, with responses from 80 participants. This supported a 20% relative reduction as the minimum required to be considered clinically meaningful. This corresponds to an intervention arm readmission rate of 34.4%. As the 30-day and 90-day rates are not consistent with an exponential time-to-event survival distribution, the log rank test was chosen for the sample size and the primary analysis. With 515 first readmission events, there is 90% power to detect a reduction from 43% to 34.4% in the 90-day reasomission rate using a two-sided log rank test at the 5% level of significance and 1:1 allocation to the goups. In the absence of withdrawals, 1331 participants would be required. This was inflated to a sample size of 1400 participants randomised, representing a 5% participant withdrawal rate, and this is expected to maintain the target of 515 events. The randomisation is stratified but the primary analysis will use the log rank test, for simplicity and to match the sample size calculation, as the purpose of the stratifiers is predominantly as foundation for subgroup analyses given that the large sample size limits chance confounding effects.

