7. ASSIGNMENT OF INTERVENTIONS

7.1 RANDOMISATION METHOD

The method of randomisation in the trial is stratified randomisation with two stratifiers defined by COPD hospitalisations (severe exacerbation) in the last year and previous exacerbations (moderate or severe) in the last year and (excluding the index hospitalisation).

- I) Prior versus no prior severe exacerbations in the last year
- II) >=2 or <2 moderate/severe exacerbations in the last year

Randomly permuted blocks will be used within the four strata defined by the categories of these stratifiers.

Severe exacerbation is defined as a COPD exacerbation requiring hospitalisation, moderate exacerbation is defined as a COPD exacerbation that is treated with steroids and/or antibiotics, but that does not require hospitalisation.

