13.4 STATISTICAL METHODS FOR PRIMARY AND SECONDARY OUTCOMES

13.4.1 STATISTICAL METHODS FOR PRIMARY OUTCOME

The log-rank test will be used to test the null hypothesis of no difference in readmission-free survival distributions between arms at the two-sided 5% significance level. These data will be collected primarily from HES. If HES data is not available, then other sources of data will be used (patient-reported data, SAE forms). These distributions will be described using the Kaplan-Meier plot. The univariate Cox proportional hazards model will be used to estimate the unadjusted hazard ratio with 95% confidence interval. In our previous meta-analysis, comorbidities, previous exacerbations and hospitalisation, and increased length of stay were significant risk factors for 30-day and 90-day all-cause readmission after an index hospitalisation with an exacerbation of COPD. Chance confounding effects are not expected given the planned size of the trial and the number of events. We will however secondarily adjust for the randomisation stratifiers as main effects within the Cox model framework. This model will be extended to explore the consistency of the primary outcome result across categories of the randomisation stratifiers, and other subgroup variables defined in the statistical analysis plan. This will involve including the interaction of a subgroup variable with study arm, Randomised controlled intervention effects within subgroup categories will be estimated with 95% confidence intervals.

We will seek to idenstify an appropriate survival distribution, in order to favilitate the development of predicted probabilities of readmission and to estimate key readmission duration quantiless. The proportionality of hazards assumption will be assessed using recommended methods²⁶. The noninformative censoring assumption will be assessed in a sensitivity analysis, where the censoring of the 90-day all-cause first readmission, by a COPD-related death, is dealt with as a composite outcome. Departures from assumptions, and consequently required analysis methods will be desribed in the statistical analysis plan.

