13.4.2 STATISTICAL METHODS FOR SECONDARY OUTCOMES

13.4.2.1 CONTINUOUS OUTCOMES

In secondary continuous outcome analyses, each randomisation stratifier and the baseline of the outcome, will be analysed as a main effect covariate and, if necessary, using the missing indicator method. Each repeated-measures continuous outcome timepoint will be analysed using linear mixed effects models with unstructured correlation structure and with covariates, including arm, interacted with time. This beneficially includes partial responses of the outcome over time because the estimated correlations between the repeated measures act equivalently to impute missing responses applying a "missing at random" assumption given the data included in the model. As nonresponse could instead be "not missing at random", the impact of this assumption will be investigated according to available collected reasons for withdrawal and missing responses, by means of sensitivity analysis in all randomised participants across a realistic range of values for the intervention effect amongst non-responders. Details of these, and any sensitivity analyses, will be described in the approved statistical analysis plan.

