13.6 METHODS FOR PRE-SPECIFIED SUBGROUP ANALYSES

Below are details of two pre-specified sub-group variables:

- i) Prior versus no prior severe exacerbations in the last year (excluding the index exacerbation)
- ii) >=2 or <2 moderate/severe exacerbations in the last year (excluding the index exacerbation)

The hypothesis is that the first category of each of these subgroup variables is related to worse outcomes, more precisely a higher rate of hospital re-admission. The subgroup analysis will investigate the consistency of the randomised intervention effect on the primary outcome analysis across these subgroup categories.

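### The primary log-rank test and main hazard ratio leave out the four randomisation strata that the protocol expects to predict readmission, giving up a small gain in calibration and power

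*Protocol*

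**What the plan says.** Section 7.1 sets the allocation: "Randomly permuted blocks will be used within the four strata defined by the categories of these stratifiers". The two stratifiers are prior versus no prior severe exacerbation, and two or more versus fewer than two moderate or severe exacerbations, both in the last year and excluding the index admission.

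Section 13.3 fixes the primary test: "The randomisation is stratified but the primary analysis will use the log rank test, for simplicity and to match the sample size calculation". It adds that the stratifiers mainly serve as the basis for subgroup analyses, and that the large sample limits chance confounding. Section 13.4.1 sets the estimate: "The univariate Cox proportional hazards model will be used to estimate the unadjusted hazard ratio with 95% confidence interval". The strata enter only afterwards: "We will however secondarily adjust for the randomisation stratifiers as main effects within the Cox model framework".

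The protocol expects the strata to matter. In section 13.4.1, its previous meta-analysis found that "comorbidities, previous exacerbations and hospitalisation, and increased length of stay were significant risk factors for 30-day and 90-day all-cause readmission". Section 13.6 expects the same of the stratifiers in their role as subgroup variables: "the first category of each of these subgroup variables is related to worse outcomes, more precisely a higher rate of hospital re-admission". For continuous secondary outcomes, section 13.4.2.1 does adjust: "each randomisation stratifier and the baseline of the outcome, will be analysed as a main effect covariate".

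**The concern.** Blocking within strata keeps the arms nearly balanced on the stratifiers, so the arm comparison varies less from trial to trial than under simple randomisation. The unstratified log-rank test computes its variance as if that restriction were absent. If the strata predict readmission, the variance is overstated and the test is conservative. A larger sample does not remove this. The protocol's argument about chance confounding concerns imbalance, which blocking already controls, and does not touch the variance.

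The stake is modest: an actual type I error a little below 5%, and some power left unused that would cost no extra patients or data. Because the protocol fixes the test and gives its reasons, this is not a detail left to the SAP. A secondary adjusted model cannot rescue a primary p-value just above 0.05, and the choice cannot credibly be changed once outcomes by arm have been seen.

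**Working it through.** **Reproducing the sample size (inputs from section 13.3).** Control risk 43%, intervention risk 34.4%, two-sided 5%, 90% power, 1:1 allocation.

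- Hazard ratio: ln(1 − 0.344)/ln(1 − 0.43) = ln(0.656)/ln(0.57) = 0.750.
- Freedman events: (1.960 + 1.282)² × ((1 + 0.75)/(1 − 0.75))² = 10.507 × 49 = 514.9, so 515.
- Mean risk (0.43 + 0.344)/2 = 0.387; 515/0.387 = 1330.7, so 1331.
- Withdrawals: 1331/0.95 = 1401 and 1331 × 1.05 = 1398, against 1400 stated.

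The sample size is sound.

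**Assumptions for the comparison.** The documents give neither stratum shares nor prognostic hazard ratios, so both are varied.

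- Shares, in the order no severe/<2, no severe/≥2, severe/<2, severe/≥2: 40/20/15/25, 55/15/15/15 and 25/25/15/35%.
- The hazard ratios of the two stratifiers multiply in the last stratum.
- N = 1332, permuted blocks of 4 within strata, daily ties, censoring at day 90.
- Hazard constant on days 0-30 and 30-90, solved so that the overall control risks are 23% at 30 days and 43% at 90 days, as in section 13.3.
- Treatment hazard ratio within strata solved so that the overall intervention risk is 34.4%.
- 100,000 null and 100,000 power runs per setting (Monte Carlo standard error about 0.07 and 0.09 points).

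**Example of the solving step** (shares 40/20/15/25, hazard ratio 1.5 each). The multipliers m are 1, 1.5, 1.5 and 2.25. Solving Σ p(1 − exp(−H·m)) = 0.43 gives H = 0.390 and control risks of 32.3%, 44.3%, 44.3% and 58.4%. Solving Σ p(1 − exp(−g·H·m)) = 0.344 gives g = 0.744, the within-stratum hazard ratio that corresponds to the marginal 0.750.

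**Results** (ranges are over the three sets of shares):

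| Hazard ratio | Type I error, unstratified | Type I error, stratified | Power gain, stratified |
|---|---|---|---|
| 1.0 each | 5.0-5.1% | 5.0-5.1% | none (90.3% for both) |
| 1.2 each | 5.0% | 5.0-5.1% | 0.1-0.2 points |
| 1.3 each | 4.8-4.9% | 5.0-5.1% | 0.3 points |
| 1.5 each | 4.5-4.7% | 5.0-5.1% | 0.7-0.8 points (about 91% to 91.6-91.8%) |
| 2 each (upper bound) | 3.6-3.7% | 4.9-5.1% | 1.7-2.3 points (92% to 93.5-94.3%) |

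The two stratifiers overlap, so the case where only prior severe exacerbation is prognostic was also run. The gain is 0.3 points at a hazard ratio of 1.5 and 0.9 points at 2 (type I error 4.3-4.6% against 4.9-5.1%). The 2-each case needs control risks of about 22-30% in the lowest stratum and 63-76% in the highest. Unstratified power is at least 90.3% in every setting.

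**Check on the mechanism.** The null variance of the unstratified z is about 0.98-0.99 at 1.3 each, 0.96-0.97 at 1.5 each and 0.88 at 2 each; for the stratified z it is about 1.00. A variance of 0.965 gives an actual error of 2Φ(−1.96/√0.965) = 2Φ(−1.995) = 4.6%. A variance of 0.88 gives 2Φ(−2.089) = 3.7%. Both match the table.

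**Check under other assumptions.** With constant hazards, shares of 40/10/20/30% or 55/15/15/15% and 20,000 runs per setting, hazard ratios of 1.5 each give type I error 4.3-4.6% unstratified against 4.9-5.1% stratified, and power 90.6-91.0% against 91.4-92.0%.

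**How often the decision changes.** At 1.5 each, the stratified test alone is significant in 0.9-1.1% of trials and the unstratified test alone in 0.2-0.3%.

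**The case against.** The strongest reply is that nothing here is wrong. The protocol makes an open, pre-specified choice that controls type I error and meets its power target. It also plans a Cox model with both stratifiers and stratifier-by-arm interactions. Every non-zero loss rests on assumed hazard ratios, because the protocol says only that the stratifiers raise readmission and not by how much. Stratifier entries cannot be amended in the randomisation system (section 9.3), so misclassification would dilute their prognostic strength and push the gain to the low end. All of this stands, and it limits the size of the point.

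Much of the power gain is also the calibration effect seen from the other side. At 1.5 each, in a 20,000-run check with shares 40/20/15/25, setting the unstratified test to a true 5% raises its power from 90.8% to 91.4-91.5%, against 91.7% for the stratified test. Only about 0.2-0.3 points is then efficiency proper. That stands too, although the planned test would be used at its nominal level, so the whole difference is what the trial forgoes.

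The change is not entirely without cost: the target in section 13.3 is marginal (43% to 34.4%), and a stratified or adjusted hazard ratio is conditional on the strata. For the same reason, the contrast with the continuous outcomes is not exact, since adjusting a linear model leaves the mean difference unchanged as a target. The binary-outcome section (13.4.2.2) mentions no stratifiers, so the protocol has no general adjustment rule that the primary analysis breaks.

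The protocol's stated reasons do not outweigh the change. Matching the sample size is no obstacle, because the same 515 events give at least the planned power with a stratified test. Simplicity amounts to one term in the code. Use of the stratifiers for subgroups does not remove their effect on the test's variance.

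**Conclusion.** The concern holds as a point of calibration and efficiency, not of validity. The primary analysis omits strata that constrain the allocation and that the protocol expects to be prognostic. The loss is small. At hazard ratios of 1.2-1.3 per stratifier, type I error is 4.8-5.0% and 0.1-0.3 points of power are forgone. At 1.5 these become 4.5-4.7% and 0.7-0.8 points. The 1.7-2.3 points at 2 per stratifier are an upper bound. If the stratifiers do not predict readmission, nothing is lost. The sizes rest on assumed stratum shares, prognostic hazard ratios, block size and hazard shape; the direction needs only that the strata are prognostic. The change is worth making because it costs almost nothing now, but the trial is sound without it.

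**What to change.** In sections 13.3 and 13.4.1:

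- Make the primary test the log-rank test stratified by the four randomisation strata.
- Make the primary estimate the Cox hazard ratio stratified by, or adjusted for, the same strata, and label it as conditional on them.
- Keep the unstratified log-rank test and unadjusted hazard ratio as supportive analyses, with Kaplan-Meier 90-day risks by arm, so that the result can still be read against 43% versus 34.4%.
- Leave 515 events and 1400 participants unchanged.
- Make the change before anyone has seen outcome data by arm.

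The cost is two sentences and one strata term in the code, with no added patients or data, since the strata are recorded at randomisation. The one trade-off is the conditional headline hazard ratio: about 0.748 at 1.3 per stratifier and 0.744-0.745 at 1.5, against the marginal 0.750.

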13.4 STATISTICAL METHODS FOR PRIMARY AND SECONDARY OUTCOMES

13.4.1 STATISTICAL METHODS FOR PRIMARY OUTCOME

The log-rank test will be used to test the null hypothesis of no difference in readmission-free survival distributions between arms at the two-sided 5% significance level. These data will be collected primarily from HES. If HES data is not available, then other sources of data will be used (patient-reported data, SAE forms). These distributions will be described using the Kaplan-Meier plot. The univariate Cox proportional hazards model will be used to estimate the unadjusted hazard ratio with 95% confidence interval. In our previous meta-analysis, comorbidities, previous exacerbations and hospitalisation, and increased length of stay were significant risk factors for 30-day and 90-day all-cause readmission after an index hospitalisation with an exacerbation of COPD. Chance confounding effects are not expected given the planned size of the trial and the number of events. We will however secondarily adjust for the randomisation stratifiers as main effects within the Cox model framework. This model will be extended to explore the consistency of the primary outcome result across categories of the randomisation stratifiers, and other subgroup variables defined in the statistical analysis plan. This will involve including the interaction of a subgroup variable with study arm, Randomised controlled intervention effects within subgroup categories will be estimated with 95% confidence intervals.

We will seek to idenstify an appropriate survival distribution, in order to favilitate the development of predicted probabilities of readmission and to estimate key readmission duration quantiless. The proportionality of hazards assumption will be assessed using recommended methods²⁶. The noninformative censoring assumption will be assessed in a sensitivity analysis, where the censoring of the 90-day all-cause first readmission, by a COPD-related death, is dealt with as a composite outcome. Departures from assumptions, and consequently required analysis methods will be desribed in the statistical analysis plan.

Survival analysis methods will be used for the outcome of the number of days alive and out of hospital at day 90I, which may be censored, and for other time-to-event secondary outcomes. Strategies to minimise missing data include obtaining primary outcome dates from more than one source, capturing this in those who move outside the study area, and our PPI group having assessed questionnaire burden. Study dropout, and loss of events, are expected to be at most 5%.

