4.3.3 MEDICAL HISTORY

Relevant medical history must be recorded. If the participant is taking any medications at baseline, the relevant condition should be recorded in the medical history.

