4.3.5 CLINICAL DATA

Relevant data from the clinical episode, including blood tests, x-rays (where applicable), clinical frailty⁴³, dyspnea VAS⁴⁴, modified MRC⁴⁵ scores, treatment and length of stay will be collected and entered into the eCRF.

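### The secondary adjusted Cox model leaves out comorbidity and length of stay on a balance argument that does not address power; adding them is a cheap, small improvement, not the correction of an error

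*Protocol*

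**What the plan says.** Section 13.4.1 tests the primary outcome with an unadjusted log-rank test and estimates the effect with a univariate Cox model. It reports from a previous meta-analysis that "comorbidities, previous exacerbations and hospitalisation, and increased length of stay were significant risk factors for 30-day and 90-day all-cause readmission". It continues: "Chance confounding effects are not expected given the planned size of the trial and the number of events". The only adjusted model it then specifies is a secondary Cox model with the two randomisation stratifiers as main effects. That model is extended only by subgroup-by-arm interactions. What the section leaves to the SAP is the choice of further subgroup variables and the handling of departures from assumptions.

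The stratifiers (section 7.1) are any severe exacerbation in the last year, and two or more moderate or severe exacerbations in the last year. They cover the exacerbation and hospitalisation history but neither comorbidity nor length of stay.

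Both other factors are collected. On medical history, section 4.3.3 says "Relevant medical history must be recorded", and Table 1 places it at screening. On the index admission, section 4.3.5 says that "treatment and length of stay will be collected and entered into the eCRF", and Table 1 places length of stay in the baseline column, which spans the three days up to discharge.

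Section 13.3 adds that the log-rank test was kept unadjusted for simplicity and to agree with the sample size calculation.

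**The concern.** The protocol identifies three groups of predictors of its primary outcome, adjusts for one, and introduces that model with a remark about chance imbalance. Imbalance is only one reason to adjust. In a Cox model, omitting a strong predictor moves the expected hazard ratio towards 1 and lowers power even if the covariate is identically distributed in both arms. A large sample does not remove that loss. The expectation of balance is therefore no reason to stop at the stratifiers.

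What is at stake is some power in the secondary adjusted analysis, from variables already in the database. The validity of the primary analysis is not at stake.

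**Working it through.** **1. The plan's own figures.** Section 13.3 states "With 515 first readmission events, there is 90% power to detect a reduction from 43% to 34.4" per cent, "using a two-sided log rank test at the 5% level of significance and 1:1 allocation".

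- Hazard ratio under proportional hazards: ln(1 − 0.344) / ln(1 − 0.43) = ln(0.656) / ln(0.57) = 0.750.
- Events by Freedman's formula: (1.960 + 1.282)² × [(1 + 0.750) / (1 − 0.750)]² = 10.51 × 49 ≈ 515. Schoenfeld's formula gives 508, and 90.4% power with 515 events.
- Participants: average risk (0.43 + 0.344) / 2 = 0.387; 515 / 0.387 = 1330.7, so 1331. This agrees with "In the absence of withdrawals, 1331 participants would be required".
- Withdrawals: "This was inflated to a sample size of 1400 participants randomised, representing a 5% participant withdrawal rate"; 1400 × 0.95 = 1330, and 1330 × 0.387 = 514.7 events.

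The unadjusted design therefore reaches its stated power without covariates.

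**2. Effect of the two omitted covariates, against a model with no covariates.** The protocol gives no prognostic strengths, so a range was assumed: a binary comorbidity covariate with 50% prevalence, and length of stay as a standard normal covariate. Each scenario used 1000 simulated trials with n = 1330, censoring at day 90, and marginal risks held at 43% and 34.4%.

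| Assumed HR: comorbidity / length of stay per SD | Power without → with | Mean HR without → with | SE of log HR without → with |
|---|---|---|---|
| 1 / 1 | 88.4% → 88.2% | 0.751 → 0.750 | 0.0888 → 0.0889 |
| 1.25 / 1.1 | 89.6% → 89.9% | 0.751 → 0.749 | 0.0888 → 0.0889 |
| 1.5 / 1.2 | 90.3% → 91.4% | 0.747 → 0.742 | 0.0888 → 0.0889 |
| 2.0 / 1.4 | 91.2% → 93.8% | 0.751 → 0.739 | 0.0889 → 0.0890 |
| 2.5 / 1.7 | 90.8% → 96.3% | 0.748 → 0.723 | 0.0889 → 0.0891 |

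Each power figure has a Monte Carlo standard error of about √(0.9 × 0.1 / 1000) ≈ 0.0095, or one percentage point. Comparisons should be made within a row, where both models are fitted to the same data.

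The standard error does not fall. The test statistic grows because the conditional hazard ratio lies further from 1. In the 2.0 / 1.4 row the mean absolute z rises from 3.222 to 3.401, and (3.401 / 3.222)² ≈ 1.11, equivalent to about 11% more information.

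A second simulation used a single normal covariate, a Weibull baseline through 23% at day 30 and 43% at day 90, and 2000 trials per setting. It gave 90.3% → 91.5%, 90.5% → 92.9% and 91.0% → 95.2% for a covariate log-hazard SD of 0.3, 0.5 and 0.7. The pattern is the same.

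**3. The comparison that matters.** The protocol already plans a stratifier-adjusted model, so the relevant gain is over that model. With comorbidity HR 1.25 to 2.0, length-of-stay HR 1.1 to 1.4 per SD, and correlation 0 or 0.3, simulation puts it at about 0.4 to 2.6 percentage points of power.

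**The case against.** The case for leaving the plan alone has several parts.

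- **Nothing is underpowered.** This stands. The 90% power belongs to the unadjusted test and reproduces.
- **The deciding test gains nothing.** This stands. With the log-rank test kept as primary, any gain falls on a secondary analysis.
- **The sentence on chance confounding is correct on its own subject, and section 13.3 gives other reasons.** Both are true. However, simplicity and agreement with the sample size calculation are reasons for the unadjusted primary test. They do not explain why the adjusted model stops at the stratifiers.
- **The SAP may add a further model.** It may, and the protocol does not forbid it. But section 13.4.1 itself names the adjusted model's content, and what it defers is subgroup variables and departures from assumptions. A factor entered as a subgroup variable would serve to examine effect modification, not to adjust the overall effect.
- **The covariates are not ready to use.** This stands in part. No comorbidity index is named, and total stay may be incomplete at randomisation. Days from admission to randomisation can replace it, but that is not exactly the predictor the meta-analysis reported and partly reflects when consent was obtained.

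A reader might infer that the plan gives up precision or that its univariate hazard ratio is biased. The documents and the calculations support neither. The standard error stays at about 0.089 with or without the covariates, and the univariate hazard ratio is a valid marginal effect. The adjusted one answers a conditional question, and the difference between them is non-collapsibility, not error.

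**Conclusion.** The point holds as a modest improvement. The protocol names comorbidity and length of stay as predictors of its primary outcome and collects both, but specifies its secondary adjusted model without them after an argument about imbalance that does not bear on power.

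The loss is small: about 0.4 to 2.6 percentage points of power relative to the stratifier-adjusted model. This depends on assumed covariate strengths and correlations and on proportional hazards. If the covariates are weak the gain is negligible. The 5.5-point gain in the most extreme row of the table (96.3 − 90.8) is against a model with no covariates and needs hazard ratios of 2.5 and 1.7 per SD, so it should not be read as the expected benefit. The primary test, its estimate and the sample size need no change on this account.

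**What to change.** In section 13.4.1, extend the planned secondary adjusted Cox model to the two stratifiers plus a prespecified baseline comorbidity count and days from admission to randomisation. Do not use total stay: randomisation can precede discharge by up to three days in an open-label trial, so total stay may be incomplete at randomisation and could be influenced by knowledge of the allocation. Report the result as a conditional hazard ratio beside the unchanged log-rank test and univariate hazard ratio. Remove the implication that expected balance is the reason for not adjusting further.

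The cost is a short amendment to section 13.4.1, carried into the SAP, with no new data collection. The count must be derived from the medical history form by one rule applied across all sites, and a method is needed for the few missing baseline values. Both should be fixed before outcome data by arm are seen.
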